Ninety patients will be randomized with equal allocation to the two arms. Randomization will be stratified by whether the baseline global QOL score is < 60 or ≥ 60 , where QOL is measured by the EORTC QLQ-C30 scale. We anticipate that approximately 10% of the accrued patients will withdraw before 1 month, leaving 80 evaluable patients to be used in the statistical analyses. The general linear model will be used to test for an arm effect (in patients receiving PLA vs HIGRT) by regressing change across time in QOL on arm, controlling for the baseline value of QOL, Child Pugh score, and time between baseline and end of treatment. To calculate the power of the arm effect (in patients receiving PLA vs HIGRT) on change in QOL, we first note that the standard deviation of a normally distributed change score (SD_C) depends upon the SD of the pre-score, the SD of the post-score, and the Pearson correlation (ρ) between the two scores. If the SD's of the pre-score and the post-score are assumed equal and the correlation between them is 0.50, then $SD_C = SD$. For purposes of the power calculation we assume that $SD=10$ and $\rho = 0.5$; therefore $SD_C = 10$. Assuming 40 evaluable patients per arm, the two-sample t-test (1-sided alpha = 0.10) of an arm difference in change across time in QOL has power 0.82 when the true arm difference in change score is 5 (i.e., 50% of SD_C). An arm difference of 50% of a standard deviation of an outcome variable is generally considered to be a "medium"-sized effect. In order to have 40 evaluable patients per treatment arm, 90 patients will be accrued (assuming drop out prior to the 1 month EORTC QOL-C30 questionnaire).

After randomization, patients may decline the randomized treatment but will continue to be evaluable for all study outcomes if treated with MWA or HIGRT. All endpoints will be analyzed per randomized arm and per treatment delivered. If the patient does not receive either SBRT or MWA, the patient will be withdrawn from the study.

Secondary Endpoints:

[figure not shown]

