1. *To estimate the change in QOL in patients receiving PLA vs HIGRT, as measured by EORTC C-30, from baseline to 3 months post-treatment.* The mean difference between arms in change from baseline to 3 months in QLC-C30 will be estimated with their 95% confidence intervals [CI]. To calculate these CI's, the mean arm difference in QOL and its standard error will be estimated from a general linear model in which change in QOL is regressed on arm, controlling for the baseline value of QOL and the Child Pugh score.
2. *To estimate the change in QOL in patients receiving PLA vs HIGRT, as measured by EORTC C-30, from baseline to 6 months post-treatment.* The mean difference between arms in change from baseline to 6 months in QLC-C30 will be estimated with their 95% confidence intervals [CI]. To calculate these CI's, the mean arm difference in QOL and its standard error will be estimated from a general linear model in which change in QOL is regressed on arm, controlling for the baseline value of QOL and the Child Pugh score.

3. *To estimate the change in QOL as measured by FACT-Hep in patients receiving PLA vs HIGRT.* Change in FACT-Hep score from baseline to 1 month, baseline to 3 months and baseline to 6 months will be calculated for each patient, and the mean arm difference in change will be estimated with its 95% CI. The CI will be estimated as described for Secondary Objective 1.
4. *To estimate grade ≥ 2 acute toxicity within 90 days of treatment initiation.* CTCAE version 4 will be used for all toxicity assessments. The acute toxicity rate will be defined as any grade 2+ toxicity occurring during treatment through 90 days post-PLA or post-HIGRT. The acute toxicity rate with its exact 95% confidence interval will be estimated within each arm. The arm difference in acute toxicity rate will be estimated with its 95% CI. We will also estimate the rate of hospitalization due to treatment complications with its 95% CI and the proportion of patients requiring treatment breaks longer than 7 days from HIGRT, with its 95% CI.

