7.3 Data collection for Quality of Life Surveys (Appendix)

Two surveys will be used to collect baseline, 1 month, 3 month and 6 month QOL information. European Organization for Research and Treatment of Cancer Quality of Life Questionnaire Core-30 (QLQ-C30) will be used to assess general symptom burden, social, financial and psychological burden. The Functional Assessment of Cancer Therapy-Hepatobiliary (FACT-Hep) survey will be used to assess liver specific symptom burden. Both surveys will be collected at baseline (prior to initiation of any therapy) and at 1, 3 and 6 month time marks. Good faith effort will be made to collect survey data in person and on paper if at all possible. If in person or on paper survey collection is not possible, oral survey data collect is allowed by authorized study staff either in person or on the phone. Good faith effort to collect data will allow that surveys may be mailed to subjects. Alternatively surveys may be completed via a secure link electronically. Surveys will be collected within a 2 week period of the planned time mark.

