7.4 Definition of Evaluable Subjects, On Study, and End of Study

Patient are “on study” during the intervention time period (either ablation or HIGRT) and the 6-month follow up while additional survey data is being collected. End of study is defined as 180 days post-therapy (+/- 30 days) at the time of the last follow up survey. We will continue to collect patient data from the EHR for 5 years after study enrollment or until death. For the purposes of the primary endpoint of QOL, a patient who has received either ablation or HIGRT and completed at least the baseline and month 1 follow up QOL surveys will be analyzed.

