10.7.2 Follow-up Requirements for Early Withdrawal

Subjects who withdraw prior to study completion will be followed for primary and secondary end points via an intention to treat analysis. All attempts will be made to complete QOL surveys as appropriate.

Subjects may decline to complete surveys at any time during study participation; declining to complete surveys will be recorded and will not be considered a reportable protocol deviation.

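### The month-3 and month-6 QOL differences come from separate single-visit models that leave earlier post-baseline scores unused; one repeated-measures model per instrument would be a free improvement

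*Combined protocol and SAP*

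**What the plan says.** Under Secondary Endpoints 1 and 2 in Section 4, the month-3 and month-6 QLQ-C30 differences are each obtained by fitting a separate "general linear model in which change in QOL is regressed on arm", with baseline QOL and Child Pugh as the only other covariates. There is one such model for each time point. For FACT-Hep at months 1, 3 and 6, "The CI will be estimated as described for Secondary Objective 1".

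The data for a joint analysis will exist. Section 7.3 states: "Both surveys will be collected at baseline (prior to initiation of any therapy) and at 1, 3 and 6 month time marks".

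On missing surveys the plan says three things:
- Section 7.4 limits the primary analysis to treated patients who "completed at least the baseline and month 1 follow up QOL surveys will be analyzed". That sentence concerns the primary endpoint only.
- Section 10.7.2 states: "Subjects who withdraw prior to study completion will be followed for primary and secondary end points via an intention to treat analysis". It also promises attempts to obtain the surveys.
- The same section adds: "Subjects may decline to complete surveys at any time during study participation".

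No section says how a missing month-3 or month-6 score enters the analysis. No imputation, longitudinal model or missing-data sensitivity analysis for QOL is described.

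**The concern.** A change score to month 6 does not exist without the month-6 survey. A patient who answered at months 1 and 3 and then stopped therefore contributes nothing to the month-6 estimate, although those two scores may explain why the patient stopped.

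Several parts of the plan make QOL-related dropout plausible. Section 10.7.1 lists adverse events and disease progression among the reasons for withdrawal by the investigator, and surveys may be declined at any time. Under Primary Endpoint, Section 4 expects a larger month-1 fall in global QOL with PLA than with HIGRT. If low month-1 scores lead to non-return, the PLA arm would lose more of its low scorers, and the completers would make PLA look better at months 3 and 6 than it was.

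At stake are secondary objectives 1 and 2 and the month-3 and month-6 parts of objective 3.

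**Working it through.** **1. The plan's own figure.** Inputs from Section 4: 40 evaluable per arm, difference 5, SD 10, correlation 0.5, hence SD of change 10, one-sided alpha 0.10.

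Standardised difference = 5 / (10 × √(2/40)) = 2.236. Power = Φ(2.236 − 1.282) = 0.830; the exact t calculation on 78 df gives 0.827. The stated 0.82 is reproduced. It concerns month 1, so it fixes the SD and correlation used below and does not bear on months 3 and 6.

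**2. Precision, for scale.** The baseline-adjusted residual SD is 10 × √(1 − 0.5²) = 8.66. The 95% CI half-width is t × 8.66 × √(2/n): about 3.9 points at 40 per arm and 4.3 at 32 per arm.

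**3. How the bias arises.** With equal correlation ρ between all visits, the slope of month 6 on month 1, given baseline, is (ρ − ρ²)/(1 − ρ²) = ρ/(1 + ρ). This is 0.33 at ρ = 0.5 and 0.41 at ρ = 0.7. The bias in the arm difference is roughly this slope times the between-arm difference in how far completers exceed their whole arm at month 1, given baseline. If that excess is equal in both arms, it cancels.

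**4. Large-sample simulation.** From the plan: SD 10 and ρ = 0.5. Assumed: the same ρ between later visits, ρ = 0.7 as an alternative (in brackets), mean 60, 300,000 per arm, and every dropout rule. The rule is P(missing) = 1/(1 + exp(−(a − s·z))) with z = (score − 60)/10. Entries are the month-6 difference, HIGRT minus PLA. The comparison column also uses the month-1 score, which is what a repeated-measures model would do here. Child Pugh was not simulated. Simulation error is about 0.03.

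| Dropout depends on | Missing PLA / HIGRT | Truth | Separate model | Using month 1 |
|---|---|---|---|---|
| Baseline only; s = 1.5, a = −1 / −2.5 | 33% / 14% | 5 | 4.98 [4.99] | 4.98 [4.99] |
| Month 1, one rule (s = 1, a = −1.5), arms equal at month 1 | 22% / 22% | 0 | −0.01 [−0.03] | −0.01 [−0.03] |
| Month 1, same rule, month-1 difference 5 | 30% / 22% | 5 | 4.85 [4.83] | 5.02 [4.98] |
| Month 1, steeper rule (s = 2), month-1 difference 5 | 42% / 28% | 5 | 4.56 [4.62] | 4.98 [5.00] |
| Month 1 in PLA only (s = 1 / 0), month-1 difference 5 | 30% / 18% | 0 | −0.69 [−0.57] | −0.04 [−0.02] |
| Month 1, unequal rates (s = 1.5, a = −1 / −2.5), month-1 difference 5 | about 46% / 14% | 5 | 4.12 [4.25] | 4.97 [5.00] |
| Unseen month-6 score, one rule (s = 1, a = −1.5) | 30% / 22% | 5 | 4.47 [4.64] | 4.52 [4.70] |
| Unseen month-6 score, unequal rates (s = 1.5, a = −1 / −2.5) | 46% / 14% | 5 | 2.47 [3.21] | 2.71 [3.48] |

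The first two rows show no bias. The next four show bias that using month 1 removes. The last two show bias that it barely reduces.

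**5. Trial-sized simulation.** Assumed: 45 per arm, true month-6 difference 3, correlation 0.5 with baseline and 0.6 between later visits, 25% missing, dropout slope 1.5 per 10 points on the previous score in both arms. The separate model gives:
- 2.99 for true differences of 0, 0 and 3 at months 1, 3 and 6;
- 2.85 for 3, 3 and 3;
- 2.71 for 5, 4 and 3.

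A further run (45 per arm, SD 10, 17-26% missing) gave 2.60 to 2.87 against a truth of 3 when early arm differences existed, a bias of 0.13 to 0.40. It gave −0.95 against a truth of 0 when only PLA had QOL-driven dropout. The joint model stayed near the truth, with a standard error 0-4% smaller. Coverage of the 95% CI was about 93-95%.

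**The case against.** The strongest reply is that the effect is small. Under a shared dropout rule the bias is at most about 0.4 points on a 0-100 scale, roughly 0.2 of a standard error (0.4/2). Coverage barely moves, and the gain in precision is slight. The affected endpoints are secondary, reported as estimates with intervals, and no test or decision rests on them. The plan also works to limit missing surveys: Section 7.3 allows telephone, mailed and electronic completion. All of this stands, and it sets the weight of the point. None of it is a reason to prefer the separate models.

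A reader might infer more than the documents support:
- **That dropout of sicker patients biases the estimates in general.** It does not. Baseline QOL is a covariate, and dropout driven by it leaves the arm difference unbiased. So does dropout driven by month-1 QOL under one rule when the arms do not differ before month 6.
- **That the plan prescribes complete-case analysis at months 3 and 6.** The completer definition in Section 7.4 covers the primary endpoint. For later visits it is only implied by the form of the model.
- **That heavy attrition is expected.** About 10% loss is projected before month 1 and nothing after. The 81% one-year survival in the Appendix covers all of Child-Pugh class B, while Section 6.2 excludes B9; class A is given as 100%.
- **That a repeated-measures model settles the matter.** It does so only if data are missing at random. When dropout follows the unseen score, it recovers little.

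**Conclusion.** The point holds as a conditional one. The separate models leave usable scores out, and the month-3 and month-6 arm differences are biased if dropout depends on post-baseline QOL and the arms differ in that QOL or in the dropout rule. The plan's own hypothesis of a larger month-1 fall with PLA makes the condition plausible. If low scorers then drop out, the advantage of HIGRT would be understated.

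With 17-26% missing (an assumption), the bias is about 0 to 0.4 points under a shared rule and about 1 point if only one arm has QOL-driven dropout, against a standard error of about 2. Heavier or more unequal dropout would enlarge it, but the documents project none. The sizes rest on SD 10 and on assumed correlations, early arm differences and dropout rules. They apply to the QLQ-C30, since the plan gives no SD for FACT-Hep.

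The primary month-1 test and the month-1 FACT-Hep estimate have no earlier post-baseline visit to discard, so they are not affected in this way. This is a free improvement and does not put the trial's main conclusion at risk.

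**What to change.** In Section 4, Secondary Endpoints 1 to 3, replace the separate models with one repeated-measures model per instrument:
- outcomes at months 1, 3 and 6;
- arm-by-visit and baseline-by-visit terms, and Child Pugh;
- unstructured covariance (three visits, so 3 × 4 / 2 = 6 parameters);
- every randomised patient with any post-baseline score, in the arm as randomised.

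Report the month-3 and month-6 contrasts with 95% CIs.

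Because this is valid only under missing at random, add a sensitivity analysis for data missing not at random, for example by lowering the expected scores of non-responders by a range of amounts, separately by arm. For scale, if 26% of one arm were missing and truly scored 5 points lower than predicted, that arm's mean would move by 0.26 × 5 = 1.3 points. Tabulate deaths and survey completion by arm and visit beside the estimates, since no model resolves QOL that is missing because of death.

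The cost is analysis-plan wording and standard software, with no new data, visits or patients. It should be settled before QOL results are examined by arm, so that the missing-data method is not chosen after the fact.

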2. PROTOCOL SYNOPSIS AND RESEARCH SUMMARY

2.1 Purpose

Given that many patients with HCC are not surgical candidates (for either resection or transplant), PLA techniques have become the standard non-operative approach. Non-randomized data have shown that the local control of HIGRT is comparable to that of PLA. Direct comparison of these two modalities via a randomized controlled clinical trial is the next logical step.

This research protocol will directly compare Percutaneous Local Ablation (PLA) to Hypofractionated Image-Guided Radiation Therapy (HIGRT) for patients with Hepatocellular Carcinoma (HCC) who are not surgical candidates or decline surgery while undergoing care at the Durham VA or at Duke Cancer Center.

Primary Objective

To compare change in Quality of Life (QOL), as defined by the European Organization for Research and Treatment of Cancer Quality of Life Questionnaire Core-30 (EORTC C-30), from baseline to 1 month post treatment in patients receiving PLA vs HIGRT.

Secondary Objectives

1. To estimate the difference in change in QOL in patients receiving PLA vs HIGRT, as measured EORTC C-30, from baseline to 3 months post-treatment
2. To estimate the difference in change in QOL in patients receiving PLA vs HIGRT, as measured EORTC C-30, from baseline to 6 months post-treatment
3. To estimate the difference in change in QOL in patients receiving PLA vs HIGRT, as measured by FACT-Hep, from baseline to 1 month, baseline to 3 months and baseline to 6 months post-treatment
4. To assess for grade ≥ 2 acute toxicity within 90 days of treatment initiation
5. To estimate the total healthcare system cost associated with PLA vs HIGRT from time of intervention through 90 days post treatment

Exploratory Objectives

1. To assess for grade 3+ late toxicity (>90 days post ablative therapy or radiation therapy)
2. To evaluate local control at the treated site within the liver
3. To evaluate distant liver recurrence (intrahepatic lesions other than treated lesion)
4. To evaluate median progression free survival (PFS)
5. To evaluate median overall survival (OS)

Hypotheses

For the primary endpoint of change in QOL at 1 month post treatment versus baseline, HIGRT will have significantly better patient reported global QOL than PLA.

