3.2 Percutaneous Localized Ablation (Microwave Ablation, control arm)

Microwave Ablation (MWA) is a form of percutaneous localized ablation using thermal ablation techniques to treat cancer via direct coagulative necrosis. Microwaves can generate high temperatures in a short period of time; MWA has the potential to improve treatment efficacy over radiofrequency ablation as it can be used to treat larger lesions and has less susceptibility to heat-sink due to vessel proximity. MWA uses electromagnetic waves (300 MHz to 300 GHz) to produce oscillation of polar molecules within tissue; this generates tissue necrosis through frictional heating. For HCC, one or more microwave antennae are inserted into the liver, usually under the guidance of ultrasonography or computed tomography (CT). Frequency and length of treatment is determined on a case by case basis depending on tumor size and proximity to vessels or other organs at risk. PLA is administered as a single treatment.

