8.8 Treatment Delivery

Ideally treatment will be delivered on consecutive days, for both the 5 and 10 fraction regimens. It is recommended that all treatment be completed in 2 weeks (for 5 fraction regimen) and 3 weeks (for 10 fraction regimen).

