10.3 Treatment Period

Treatment period will be from start to finish of HIGRT or date of ablation based on randomization. Assessment will be performed by the study key personnel at baseline then months 1, 3 and 6 post-treatment for QOL surveys. They will also undergo weekly assessment by radiation oncologist during radiotherapy.

Restaging imaging and labs (LFTs, and AFP, INR) will be performed as per standard of care for HCC (typically 1 month post-treatment, 3 months post treatment and then every 3 months thereafter). Deviations from standard of care follow up for patients are at the discretion of the treating physicians.

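### Acute toxicity is set at 90 days from treatment initiation but defined to run until 90 days after treatment ends, so HIGRT is counted for about 94 to 111 days and PLA for 90

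*Combined protocol and SAP*

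**What the plan says.** Section 2.1, Secondary Objective 4, reads "To assess for grade ≥ 2 acute toxicity within 90 days of treatment initiation". The heading of Secondary Endpoint 4 in section 4 uses the same anchor: "acute toxicity within 90 days of treatment initiation". The defining sentence under that heading is "The acute toxicity rate will be defined as any grade 2+ toxicity occurring during treatment through 90 days post-PLA or post-HIGRT". The comparison follows: "The arm difference in acute toxicity rate will be estimated with its 95% CI".

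The two treatments differ in length. Section 3.2 states that "PLA is administered as a single treatment". Section 8.6 gives HIGRT in 5 or 10 fractions over 2 or 3 weeks. Section 8.8 prefers consecutive days and adds: "It is recommended that all treatment be completed in 2 weeks (for 5 fraction regimen) and 3 weeks (for 10 fraction regimen". Section 10.3 fixes the treatment period by arm: "Treatment period will be from start to finish of HIGRT or date of ablation based on randomization".

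The adjacent endpoint has a similar problem. Late toxicity (section 4, first exploratory endpoint) is headed as more than 90 days after treatment. Its definition counts grade 3+ events from completion of the regimen up to 6 months.

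**The concern.** The objective and the definition use different clocks, and nothing in the document reconciles them. For PLA the clocks agree, because treatment starts and ends on the same day. For HIGRT they differ by the length of the course. Two analysts could therefore report different HIGRT rates from the same data, each citing the protocol.

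The definition is the sentence an analyst would program. It gives one arm more calendar time in which to have a first grade 2+ event, and the result enters a difference in proportions with no stated adjustment for time at risk. Part of any HIGRT excess could then reflect the window and not the treatment.

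**Working it through.** The plan gives no acute toxicity rate and no figure for window length, so there is no figure of its own to reproduce.

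**Step 1. Window lengths under the definition.** Let d be the days from first to last treatment. The window from first treatment is 90 + d.

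| Treatment | d (days) | Window (days) | Longer than PLA by |
|---|---|---|---|
| PLA, single treatment | 0 | 90 | – |
| HIGRT, 5 fractions, consecutive weekdays | 4 to 6 | 94 to 96 | 4/90 = 4% to 6/90 = 7% |
| HIGRT, 5 fractions, 2-week limit | 14 | 104 | 14/90 = 16% |
| HIGRT, 10 fractions, consecutive weekdays | 11 to 13 | 101 to 103 | 11/90 = 12% to 13/90 = 14% |
| HIGRT, 10 fractions, 3-week limit | 21 | 111 | 21/90 = 23% |

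Weekday delivery is an assumption. Five fractions starting on a Monday span 4 days, and any other start crosses a weekend and spans 6. Ten fractions span 11 or 13 days. Section 4 plans to count breaks longer than 7 days, and such breaks could extend d further.

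**Step 2. Direction.** For HIGRT, days 0 to 90 from initiation lie wholly inside days 0 to 90 + d. For PLA the two windows coincide. Replacing the objective's window by the definition's can add HIGRT patients with an event and cannot add PLA patients. This needs no hazard model, but it does assume that patients receive their assigned treatment.

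**Step 3. Size under a constant hazard, equal in both arms.** With p the 90-day rate, excess = 1 − (1 − p)^((90 + d)/90) − p. Because the documents give no p, a range is shown.

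| Assumed p | d = 7 | d = 14 | d = 21 |
|---|---|---|---|
| 10% | 0.7 points | 1.5 | 2.2 |
| 20% | 1.4 | 2.7 | 4.1 |
| 30% | 1.9 | 3.8 | 5.6 |
| 50% | 2.6 | 5.1 | 7.5 |

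At p = 30% and d = 21: 1 − 0.70^(111/90) = 35.6%, an excess of 5.6 points. At the shortest course, d = 4, the excess is 1.1 points.

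**Step 4. Size if events cluster early.** Assume p = 30%, with 80% of those events by day 30 (0.80 × 30% = 24%) and a constant hazard afterwards. The daily hazard after day 30 is ln(0.76/0.70)/60 = 0.00137. The excess is 0.70 × (1 − exp(−0.00137 × d)), which is 0.7 points at d = 7 and 2.0 points at d = 21.

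**Step 5. Scale.** At 40 patients per arm and a 30% rate, the 95% CI half-width for the difference is 1.96 × √(2 × 0.30 × 0.70/40) = 20 points.

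**Step 6. Late toxicity.** Under the current definitions, acute toxicity runs through day 90 after treatment and late toxicity starts at completion. A grade 3+ event in those 90 days meets both definitions, although the late heading says more than 90 days.

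**The case against.** The strongest reply is that an end-of-treatment clock may be what was meant. The late toxicity heading and the cost endpoint in section 4, the interim safety review in section 7.1.3 and the survey schedule in section 11.2 all count from the end of treatment. On that reading the word initiation is the outlier. Anchoring to initiation also has its own asymmetry: after a 21-day course HIGRT has only 90 − 21 = 69 post-completion days in the window, against 90 for PLA. This stands as a reason to offer the sponsor a choice. It does not remove the conflict, because the objective and heading would still have to change and the unequal windows would still need stating.

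The effect is also small beside the uncertainty of the estimate. The endpoint is secondary and estimation-only, and the interim safety review uses grade 4-5 events. All of that stands.

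Three stronger readings are tempting and are not supported:

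- A reader might infer that the extra HIGRT days are the most closely observed ones, since section 10.3 says "They will also undergo weekly assessment by radiation oncologist during radiotherapy". Both clocks already include the on-treatment days. What the definition adds is the tail after day 90 from first treatment, when those checks are over. Unequal contact between arms is a separate matter, and section 12.1 already requires all adverse events to be recorded from consent to end of study.
- A reader might infer that the extra days mainly add cirrhosis events unrelated to treatment. The adverse event definition in section 12.1 is broad, but the endpoint is worded as toxicity, and the plan does not say that unrelated events count.
- A reader might infer that re-anchoring merely moves tail events from acute to late. Late toxicity is grade 3+ only, so grade 2 events in those days would leave both endpoints.

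**Conclusion.** The contradiction is real and unreconciled. As defined, acute toxicity is counted for 90 days after PLA and for about 94 to 111 days from the first HIGRT fraction, longer with breaks, and the rates are then compared without adjustment. Measured against the twice-stated 90 days from initiation, this can only raise the HIGRT rate.

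For 7 to 21 extra days and an assumed 30% 90-day rate, the artefact is 1.9 to 5.6 points under a constant hazard. That is near an upper bound if, as is likely, acute events thin out with time. It falls to about 0.7 to 2.0 points if 80% of events occur by day 30. The 30% rate and both hazard shapes are assumptions. The artefact would not overturn a result whose confidence interval extends about 20 points either way, but it runs in one direction and a larger sample would not remove it. The definition should be corrected before analysis.

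**What to change.** In section 4, define acute toxicity in both arms as any grade 2+ toxicity from the first treatment day (ablation date or first fraction) through day 90 from that date, matching Secondary Objective 4 and the endpoint heading. Start late toxicity (grade 3+) on day 91 of the same clock. State which clock its 6-month end uses, because leaving that end tied to treatment completion would make the HIGRT late window longer by the length of the course.

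If the sponsor intended to count from the end of treatment, reword the objective and heading to say so, and report the window length by arm beside the arm difference. Late toxicity should still start where acute toxicity stops.

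Either route costs a sentence or two and changes neither treatment nor sample size. The initiation clock has two costs. HIGRT keeps fewer post-completion days in the acute window (about 69 after a 21-day course). Grade 2 events in the 1 to 3 weeks removed are counted in neither endpoint, and only grade 3+ events there become late toxicity.
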